Box 2. Summary of study methods

	matched on birth-year. This date will be the non-initiator comparators index-date . Thus, with regards to treatment, the active treatment arms initiate a treatment on index-date and non-initiator comparators do not.
Outcome	First recorded occurrence of SD, including the following ICD-10 codes: F52.0, F52.1, F52.2, F52.3, F52.6, F52.8, F52.9, N48.4, N94.1, N48.3 [See section 4.6, Outcome]
Follow-up	Patients will be followed-up from index-date up to maximum 1 year. Thus, patients will be followed-up from index-date to the earliest of: date of first occurrence of outcome, loss to follow-up, death (only available in IMRD UK), end of follow-up (1 year) or end of the study period [See Section 4.5, Follow-up period]
Casual contrast of interest	Intention to treat effect, i.e., patients were followed up irrespective of treatment change (main analysis).
Statistical methods	
• Inverse probability of treatment weighting (IPTW) will be used to adjust for confounders measured at cohort entry.• Incidence rates (IR) and cumulative incidence proportions will be estimated for each treatment cohort.• Hazard ratios (HRs) will be estimated using a Cox proportional hazards model.• Cumulative incidence proportions will be estimated for each treatment arm using the Kaplan-Meier estimator.• Sensitivity analyses will include a "Per-protocol" analytical strategy and adjusting for informative censoring at treatment protocol violation. 
[See Section 4.7. Statistical analyses]

115

116

117 4.1. Study design

118 Comparative cohort design, including:

119 a) Active comparator, new user design:

120 • Esomeprazole initiators (target treatment [Cohort 1]) will be compared to the following
121 comparators: pantoprazole [Cohort 3], lansoprazole [Cohort 4], and H2RAs [Cohort 5]
122 initiators.

123 • Omeprazole initiators (target treatment [Cohort 2]) will be compared to the following
124 comparators: pantoprazole [Cohort 3], lansoprazole [Cohort 4], and H2RAs [Cohort 5]
125 initiators.

126 Treatment initiation will be defined as the prescription date for PPIs/H2RAs after a washout
127 window of at least 365 days in which no previous prescription with any PPIs or H2RAs have
128 been recorded. This date will coincide with the cohort entry or start of follow-up in the study,
129 which we will refer to as **index-date**.

130 b) Non-initiator comparator

[figure not shown]

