 160 ^e Censoring: Patients will be censored at the earliest of the following events: first occurrence of outcome, loss to
 161 follow-up (e.g., transfer out date from the general practice in IMRD or end of continuous observation of the patient
 162 by the practice in IQVIA™ DA Germany, or date of last data collection from the practice), death (only available in
 163 IMRD UK), end of follow-up (1 year) or end of the study period.
 164

165 4.2. Data sources

166 The following databases will be used: IQVIA™ Disease Analyser (DA) Germany, and IQVIA™ Medical
 167 Research Data (IMRD) UK. Brief descriptions of these databases are provided in **Annex 1**.

168

169 4.3. Study population

170 The population eligible for the study will be selected based on the inclusion and exclusion criteria listed
 171 in Table 1, which will be measured at baseline (i.e., index-date). Figure 1 above provides details on the
 172 assessment windows for these eligibility criteria in relation to the index-date.

173 **Table 1.** Eligibility criteria.

Inclusion criteria	Exclusion criteria

 Patients registered with a general practice (GP) covered by IMRD or patients visiting GP in IQVIA™ DA Germany; 	
 Recorded prescription of any PPIs or H2RAs within one year before index-date;

 Male; 
AND
 
 Aged ≥18 years; 	
 Recorded history of SD OR treatment for SD (e.g., Viagra) prior index-date;

 At least one year of recorded medical history prior to index-date. 	
 Those with recorded history of selected severe CNS diseases prior index-date, namely: Hereditary ataxia (mainly hereditary spastic paraplegia), Huntington disease, spinal muscular atrophy and related syndromes, cerebral palsy, hemiplegia, paraplegia and tetraplegia, other paralytic syndromes (monoplegia of lower limb, cauda equina syndrome, locked-in syndrome), dependence on wheelchair.

 Recorded diagnosis for GERD, gastric and duodenal ulcers, chronic gastroduodenitis, and Zollinger-Ellison syndrome¹; 
OR
	--

Inclusion criteria	Exclusion criteria

 History of comedication with NSAID, acetyl salicylic and derivatives, glucocorticoids, and antithrombotic treatments ^{1, 2} 	

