174 ¹ These indications are selected indications for PPIs and H2RAs. We restricted the study population to patients with
175 chronic indications, for which treatment is likely chronic. The rationale for this is explained in Limitations (first
176 paragraph)

177 ² These are assumed to be proxies of indications (e.g., PPIs are indicated to patients requiring continued NSAID or
178 antithrombotic therapy).

179

180 **4.4. Recruitment period**

181 The recruitment period will start on January 1st, 2005, and will end on December 31st 2020 in both
182 IQVIA™ DA Germany and IMRD UK.

183 Although the first use of esomeprazole dates to September 2000, in IMRD UK and October 2000, in
184 IQVIA™ DA Germany, we opted to include data from 2005 the year when the distribution of male
185 sexual dysfunction events started being consistent.

186 Additionally, we opted to limit the recruitment period up to 2020 because the use of H2RAs is very
187 limited in IQVIA™ DA Germany after 2020. Of note, the suspension of all ranitidine medicines in the
188 European Union due to the presence of low levels of an impurity called N-nitrosodimethylamine
189 (NDMA) in April, 2020^[1] led to the suspension of ranitidine, the dominant H2RA in Europe.

[figure not shown]
190

191 **4.5. Follow-up period**

192 Patients will be followed-up from index-date up to maximum one year. For instance, patients recruited
193 in 2020 can be followed up to 2021. Thus, patients will be followed-up from index-date to the earliest
194 of: date of first occurrence of outcome, loss to follow-up (e.g., transfer out date from the general
195 practice in IMRD or end of continuous observation of the patient by the practice in IQVIA™ DA
196 Germany, or date of last data collection from the practice), death (only available in IMRD UK), end of
197 follow-up (1 year) or end of the study period.

198 Considering the recommended duration for these treatments (4-8 weeks for PPIs and 8-12 weeks for
199 H2RAs), a patient may participate with several treatment episodes - and consequently index-dates -
200 during the study period. For example, a patient may receive a prescription for 8 weeks after which the
201 medication is discontinued to assess the need for ongoing therapy (on-demand or intermittent use).
202 After 15 months of discontinuing this therapy, the patient may receive another prescription for the
203 same therapy and duration. Therefore, this patient will enter the study twice and contribute with two

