 233 exposure) with any certainty. Electronic health records may not capture the entire patient
 234 history of utilisation of these treatments. In addition, these treatments are used
 235 interchangeably which would mean that a substantial number of individuals would be excluded
 236 from the study population if the study focuses only on first use ever of any of these
 237 substances. Therefore, the study will assess initiation of treatment after a washout window of
 238 at least 365 days.

239 Prescriptions will be identified through keyword searches using international non-proprietary
 240 names (INNs) in several prescription-related variables (e.g., "Therapy Name", "Product Name",
 241 "Molecule"). Detailed list of keywords used are provided in **Annex 2**.

242 PPIs will include the most prescribed substances in each database, i.e., esomeprazole,
 243 omeprazole, and pantoprazole in IQVIA™ DA Germany, and esomeprazole, omeprazole, and
 244 lansoprazole in IMRD UK. Other PPIs such as dexlansoprazole and rabeprazole are less
 245 commonly recorded in the selected databases and, therefore, will not be included in this study.

246 Products containing H2RAs will include the following substances (ordered by frequency of
 247 prescribing): ranitidine, famotidine, nizatidine, cimetidine in IMRD, and ranitidine, famotidine,
 248 cimetidine, nizatidine in IQVIA™ DA Germany.

249 **Annex 2** provides details on the use of PPI and H2RA substances over time in each database.

250

251 b) Non-initiators arm (cohort)

252 Non-initiator comparators will be randomly sampled and selected on each date of the
 253 recruitment period when esomeprazole/omeprazole initiators start treatment, **matched on**
 254 **birth-year**. This date will be the non-initiator comparators index-date. Thus, with regards to
 255 treatment, the active arms initiate a treatment on index-date and non-initiator comparators do
 256 not. Matching on index-date and on year of birth is meant to ensure a similar distribution of
 257 calendar time and age at index-date, both of which are considered important potential
 258 confounders.

259 It should be noted that *non-initiators* refer to patients who have selected indications (see Table
 260 1 above, inclusion criteria) recorded in the databases but who did not initiate therapy (i.e., did
 261 not have a recorded PPIs or H2RA prescription within 12 months before index-date or on index
 262 date).

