263 Table 2 summarises the treatment assignments by cohorts.

264

265 **Table 2.** Treatment assignment by cohorts.

Target treatments:	Active comparators:	Non-initiator comparator:

 • Treatment initiation as monotherapy* with: 
 ○ Esomeprazole [Cohort 1] 	
 • Treatment initiation as monotherapy* with: 
 ○ Selected PPIs: 	
 • Prior diagnosis of indication but no treatment

Target treatments:	Active comparators:	Non-initiator comparator:

 ○ Omeprazole [Cohort 2] 	
 ▪ Omeprazole [Cohort 2], when esomeprazole is the target treatment; ▪ Esomeprazole [Cohort 1], when omeprazole is the target treatment; ▪ Pantoprazole in IQVIA™ DA Germany [Cohort 3], or ▪ Lansoprazole in IMRD UK [Cohort 4] ○ Selected H2RAs [Cohort 5]: ranitidine, famotidine, cimetidine, nizatidine in IQVIA™ DA Germany, and ranitidine, famotidine, nizatidine, cimetidine in IMRD UK. 	
initiation with either PPIs nor H2RAs within previous 12-month or on index date [Cohort 6].

266 * **Note:** Treatment initiation with any combination with other PPIs or H2RAs on the index-date is not part of the
267 study.

268
269 **Outcome**

270 Sexual dysfunction (SD) will be defined as the first recorded occurrence of any of the following
271 conditions (ICD-10 code): lack or loss of sexual desire (F52.0); sexual aversion and lack of sexual
272 enjoyment (F52.1); failure of genital response (F52.2); orgasmic dysfunction (F52.3); nonorganic
273 dyspareunia (F52.6); other sexual dysfunction, not caused by organic disorder or disease (F52.8);
274 unspecified sexual dysfunction, not caused by organic disorder or disease (F52.9); impotence of
275 organic origin (N48.4); dyspareunia (N94.1), priapism, painful erection (N48.3).

276 **Annex 2** provides the list of WHO ICD-10 codes used to identify outcome events in IQVIA™ DA
277 Germany. READ codes were used to identify these conditions in IMRD UK (Annex 2). Of note, SD as
278 defined here is mostly driven by erectile dysfunction/impotence, which is the most frequent condition
279 recorded in both databases.

280
281 **Potential confounding factors:**

282 Analyses will account for the following baseline covariates measure before index-date, which are

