417 another treatment was initiated. It should be noted that, in the analysis comparing with non-initiators,
418 we restricted the study population to patients with chronic indications, for which treatment is likely
419 chronic.

420 To our knowledge, the accuracy of diagnostic coding for sexual dysfunction has not been assessed in the
421 primary care databases available. However, the nature of the diagnosis means that its recording in
422 primary care records could be reasonably accurate, particularly for sexual dysfunction in male individuals.
423 Nonetheless, this assumption should be treated cautiously. In the UK, the patent for Viagra expired in
424 June 2013, which followed a drop by 93% in the price of generic preparations of sildenafil compared to
425 the price of branded Viagra (Connelly, 2017). Besides, Sildenafil has been available OTC without
426 prescription from UK pharmacies since 2017 and, therefore, patients have no longer needed to see their
427 doctor to get a diagnosis ever since. (MHRA, 2017) These events led to marked changes in diagnosis
428 coding practices of erectile dysfunction during 2013-2014 and marked decrease of coding for impotence
429 by GPs since 2017 which are reflected in the distribution of outcome events over calendar time. In
430 IQVIA™ DA Germany the reporting of male sexual dysfunction appears stable after 2005. To account for
431 uncertainties around potential misclassification due to changes in diagnostic criteria or coding practices
432 over time, calendar period will be adjusted for in the analysis.

433 It also needs to be considered that patient's medical history, as captured by GP practices included in
434 the study, may be incomplete, particularly in the IQVIA DA Germany database. In Germany, there is
435 no mandatory GP system and patients have free doctor choice. A specialist can be consulted without
436 referral from the GP. As a result, data are collected from visits to various medical practices which are
437 not linked by a unique patient identifier. Therefore, the entire medical history of patients might be
438 fragmented and for that reason there is a risk of exposure, outcome and covariates misclassification.
439 However, this misclassification will affect both target and comparator groups.

440 Although confounding by indication represents a common source of bias, it is not likely that the main

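### Non-initiator contrasts: initiators enter at a prescribing contact, non-initiators need none, and consultation frequency is not adjusted for, so detection pushes these hazard ratios upward

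*Protocol*

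**What the plan says.** **Entry, active arms.** Section 4.1 defines initiation as a prescription date after a washout of at least 365 days in which no PPI or H2RA prescription has "been recorded. This date will coincide with the cohort entry or start of follow-up in the study".

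**Entry, non-initiators.** Section 4.6 b) says: "Non-initiator comparators will be randomly sampled and selected on each date of the" recruitment period on which a target-drug initiator starts, with matching on birth-year. The stated purpose of the matching is balance in calendar time and age. The treatment condition is that these men did "not have a recorded PPIs or H2RA prescription within 12 months before index-date or on index" date. No consultation on or near that date is asked for.

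**Follow-up and prior outcome.** Section 4.5: "Patients will be followed-up from index-date up to maximum one year". Table 1 in Section 4.3 excludes "Recorded history of SD OR treatment for SD (e.g., Viagra) prior index-date".

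**Outcome.** Section 4.6: "Sexual dysfunction (SD) will be defined as the first recorded occurrence of any of the following" listed conditions. It is a code in practice records.

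**Adjustment.** Lists (i) to (v) in Section 4.6 cover comorbidities, drugs, age, lifestyle, BMI, past PPI/H2RA use and calendar year. They contain no count of consultations or other utilisation measure. Section 4.7.3 plans no adjustment beyond the weights, and the sensitivity analyses in Section 4.7.4 change only censoring.

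**The concern.** SD enters the data only when a man is seen and the diagnosis is coded. The protocol accepts this link: Section 4.9 notes that sildenafil has been on sale without "prescription from UK pharmacies since 2017 and, therefore, patients have no longer needed to see their" doctor for a diagnosis, and that coding by GPs then fell. An initiator has a recording opportunity on the day he enters. A non-initiator has one only by chance. If initiators are also more frequent attenders, they have more such opportunities during the year.

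The non-initiator arm carries particular weight. Section 2 and Box 1 explain that lansoprazole and the H2RAs already list impotence or erectile dysfunction, so the untreated group was added to show background risk. A detection difference would raise the hazard ratio against non-initiators for both target drugs, which is the same pattern as the suspected harm. Section 4.9 discusses OTC use, coding changes, fragmented German records and unmeasured risk factors, but not unequal detection between initiators and non-initiators.

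**Working it through.** The protocol gives no event count, contact rate or target hazard ratio, so it has no figure to reproduce. The check has a textual part and an illustration on assumed inputs.

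**Is day 0 in the risk period?** Follow-up runs from the index date, and SD history is excluded before the index date. For prior acid suppressants in non-initiators the protocol names both the period before the index date and the index date itself. For SD it names only the former. Read together, a first SD code on the index date is not an exclusion and falls inside follow-up.

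**Effect of the day-0 contact alone, true HR = 1.** Assumptions:
- *v* = contacts per year after entry, equal in both arms.
- *f* = share of SD codes that arise at visits made because of SD. These do not depend on an acid-suppressant consultation.
- The remaining codes are equally likely at any contact, and men are followed for the full year.

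With background rate λ, each ordinary contact yields (1 − f)λ/v codes. Initiators have one extra certain contact, so

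null HR ≈ [λ + (1 − f)λ/v] / λ = 1 + (1 − f)/v.

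| v per year | f = 0 | f = 0.5 |
|---|---|---|
| 3 | 1 + 1/3 = 1.33 | 1 + 0.5/3 = 1.17 |
| 5 | 1 + 1/5 = 1.20 | 1 + 0.5/5 = 1.10 |
| 10 | 1 + 1/10 = 1.10 | 1 + 0.5/10 = 1.05 |

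λ cancels. At f = 0, results were unchanged to two decimals for background rates of 0.5, 1 and 2 per 100 person-years.

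**Simulation check.** The setting was 400,000 men per arm, v = 4, f = 0 and 1 event per 100 person-years. The formula gives 1 + 1/4 = 1.25. A Cox model gave 1.27 with day 0 (5,057 versus 4,002 events) and 1.00 with day-0 cases removed. The gap from 1.25 is sampling error: the standard error of the log HR is about √(1/4,002 + 1/5,057) = 0.021, and ln(1.27/1.25) = 0.016.

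**Unequal consulting after day 0 is removed.** If initiators consult r times as often, the null HR is f + (1 − f)r. For r = 1.25 this is 1.25 at f = 0 and 0.5 + 0.5 × 1.25 = 1.13 at f = 0.5. For r = 1.5 it is 1.50 and 1.25. Removing day 0 is therefore not sufficient by itself.

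**Opposing dilution.** If a share q of non-initiators is in fact exposed, a true hazard ratio h appears as h/(1 + q(h − 1)). With h = 1.5 and q = 0.3 this is 1.5/1.15 = 1.30. With h = 1 it stays 1, so dilution masks a true effect but does not cancel a detection artefact when there is none.

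**The case against.** **Day 0 is inferred.** Section 4.1 says that Figure 1 shows the assessment windows, and the figure could not be read for this review. It, or a separate analysis plan, may already settle the matter. This stands as a qualifier. If the figure excludes day 0, the wording of Section 4.5 and Table 1 should be aligned with it. The missing contact requirement and the missing utilisation covariate would remain.

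**No contact required is not no contact.** A reader might infer that non-initiators are absent or inactive men, above all in Germany, where there is no mandatory GP registration. The documents do not support that. Table 1 calls for men visiting a GP in the German database and for a year of recorded history. Follow-up stops when the practice no longer observes the patient. Box 2 asks for recent comedication on that entry route. These rules secure observability, but they do not give non-initiators a contact at entry.

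**The size may be small.** The outcome is mostly erectile dysfunction, and many men may attend because of it. That is fair, and it is why f = 0 is an upper end and not an estimate. The f = 0.5 column is no better founded, because f is as unknown as v.

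**Weighting may help.** More than 50 covariates, many of them chronic drugs and diseases, partly stand in for how often a man consults. They cannot remove the contact on day 0.

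**Net direction.** A reader might infer that the reported HR must be too high. That does not follow. OTC use among non-initiators, acknowledged in Box 1 and Section 4.9, and later initiation under the ITT rule pull a true effect toward the null. Upward describes the detection component only.

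**Caution is already stated.** Box 1 calls the untreated group less preferable, and Section 4.9 warns of residual confounding. Neither passage mentions detection.

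**Conclusion.** The point holds for the two non-initiator contrasts, esomeprazole and omeprazole. As the text reads, entry is tied to a prescription in one arm and to a matched calendar date in the other. SD coded at the prescribing visit counts against the drug, and consultation frequency is not balanced. The resulting detection component is upward.

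Its size cannot be derived from the protocol. Under equal contact rates the day-0 part gives a null HR of 1.33 to 1.10 (f = 0) or 1.17 to 1.05 (f = 0.5) for 3 to 10 contacts a year. Any excess in consulting adds to this. Every one of these inputs is an assumption, and the figures are not estimates of the bias in this study.

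It would go too far to extend the point to the comparisons with other PPIs or H2RAs. All active arms enter on a prescription date, so those contrasts are largely unaffected. The change should be made before analysis, because the non-initiator arm is the one meant to show background risk.

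**What to change.** 1. Start follow-up on the day after the index date, and treat an SD code or SD treatment recorded on the index date as an exclusion in all arms. Align Section 4.5, Table 1, Box 2 and Figure 1.
2. Add the number of practice contacts in the 12 months before the index date to the propensity model, and report its balance with the other covariates.
3. Name residual detection bias in Section 4.9. A prior-year count will not remove extra visits that treatment itself generates.

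Optional: a sensitivity analysis in which non-initiators are drawn from eligible men with a practice contact on or shortly before the matched date. This is a design preference, since it loosens the exact date match.

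Cost: wording and minor programming on data already held, plus the loss of day-0 events. On the assumptions above, these are (1 − f)/(v + 1 − f) of initiator events. For v = 3 to 10 that is 1/4 = 25% to 1/11 = 9% at f = 0, and 0.5/3.5 = 14% to 0.5/10.5 = 5% at f = 0.5. The loss may not be trivial, but these events carry no information on the effect of a drug first prescribed that day.

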299 washout) esomeprazole versus patients who: a) initiated other proton pump inhibitors (PPIs, namely
300 omeprazole, pantoprazole/lansoprazole); b) initiated histamine type 2 receptor antagonists (H2RA))
301 and c) patients who did not initiate treatment with either PPIs or H2RA but had received a diagnostic
302 for a PPI or H2RA indication (i.e. non-initiators comparators). Outcome events will be attributed to the
303 baseline treatment protocol regardless of treatment change during follow-up. (i.e., **intention-to-treat
304 analysis (ITT)**).

305

306 4.7.2. Descriptive analysis

307 Descriptive analyses will be performed to describe the study cohorts at baseline in terms of
308 demographic characteristics, lifestyle factors, potential indications, comorbidities, and history of
309 treatment with drugs commonly associated with sexual dysfunction.

310

311 4.7.3. Main statistical analysis

312 **Inverse probability of treatment weighting (IPTW)**

313 Inverse probability of treatment weighting (IPTW) will be used to render the assignment of study
314 treatments independent of the baseline measured covariates, thus minimising the potential
315 confounding effect of these covariates.

316 Using IPTW, the average treatment effect (ATE) in the entire study population will be estimated,
317 assuming that all important confounding variables have been accounted for. For each observation in
318 the study population, the IPTW is the inverse of the probability of receiving the observed treatment

319 conditional on all variables considered sufficient for confounding adjustment. In order to stabilize the
320 weights (i.e., less extreme weights, that are closer to the mean weight of one), the numerator of one
321 will be replaced by the marginal probability of receiving the observed treatment in the study population
322 (i.e., the proportion of observations in the study population with the respective treatment). (Hernan &
323 Robins, 2006) All analyses will then be conducted in the re-weighted population without additional
324 confounding adjustment on the assumption of no unmeasured confounding. To account for weighting
325 the population (essentially multiplying observations by the weight coefficient) robust standard error
326 estimators will be used (Hernan & Robins, 2020).

327 The distributions of baseline covariates before and after weighting was compared between
328 esomeprazole and the other treatment arms by calculating and plotting standardized mean differences
329 (SMD), with a SMD of <10 used to determine appropriate covariate balance. For each variable, the
330 SMD was the difference in mean (for continuous variables) or proportion (for binary variables) between
331 each treatment arms and the entire study population (which is the target population in the ATE to
332 which the composition of covariates distribution in each treatment arm is standardized), divided by the
333 study population standard deviation of the variable. (McCaffrey et al., 2013)

334

335 **Intention-to-treat (ITT) analysis**

336 The ITT approach chosen for the main analysis will involve following patients from the date of study
337 treatment initiation (i.e., index date) until the earliest of any of the following: first outcome event date,
338 loss to follow-up (e.g., transfer out date from the general practice in IMRD or end of continuous
339 observation of the patient by the practice in IQVIA™ DA Germany, or date of last data collection from
340 the practice), date of death (only available in IMRD) or the end of the study. Consequently, outcome
341 events will be attributed to the baseline treatment regardless of treatment change during follow-up.
342 Moreover, it will be assumed that intercurrent events that may occur during follow-up are independent
343 of the risk of the outcome (i.e., the risk of experiencing the outcome among individuals remaining in
344 the analysis over the course of follow-up is representative of the risk among censored individuals).

345

346 **Incidence rates (IRs)**

347 IRs will be calculated as the number of events occurring during follow-up divided by the total person-
348 time in each treatment-arm. IRs will be presented as number of events per 100 person-years.

349

350 **Cumulative incidence (Incidence proportion)**

351 Survival (i.e., the proportion of the patients included at baseline who have not yet experienced a
352 sexual dysfunction event) over the course of follow-up will be estimated by treatment arm using the
353 Kaplan-Meier method. (Bland & Altman, 1998) The cumulative incidence will be calculated as the
354 complement of survival (i.e., the proportion of the patients included at baseline who have experienced
355 a sexual dysfunction event) at each follow-up time and will be presented as number of events per 100
356 patients.

357

358 **Cox proportional hazards model**

359 Hazard ratios of sexual dysfunction associated with treatment of interest (esomeprazole) versus
360 comparators will be estimated using a Cox proportional hazards model.

361

362 **4.7.4. Sensitivity analysis**

363 The following sensitivity analyses will be performed to test the validity of the underlying assumptions
364 and the robustness of the study findings:

365 **Applying "per-protocol" (PP) approach:** In this analysis, the follow-up of patients will be censored
366 at the initiation of a PPI or H2RA other than the baseline treatment. Assuming that such censoring is
367 independent of the risk of SD (i.e., non-informative censoring), this analysis will estimate the
368 treatment effect had patients remained on the baseline treatment for the entire follow-up or
369 discontinued the baseline treatment but without initiating an alternative PPI/H2RA.

370 Thus, we will consider a patient to respect the baseline treatment protocol from index-date to the date
371 of crossing over to an alternative treatment arm. Patients will be censored at the earliest of the
372 following events: end of index-treatment, crossing over to an alternative treatment arm, first outcome
373 event date, loss to follow-up (e.g., transfer out date from the general practice in IMRD or end of
374 continuous observation of the patient by the practice in IQVIA™ DA Germany, or date of last data
375 collection from the practice), date of death or at the end of the study period.

376 This approach addresses the situation in which a patient initiates another PPI/H2RA after index-date,
377 which might be problematic if the other PPI/H2RA initiated after index-date and within the 1-year
378 follow-up might cause the outcome event instead of the baseline treatment.

379 It should be noted that the difference between the ITT and PP approach will lie in the follow-up period.
380 The same baseline conditions such as eligibility criteria and washout period before index-date were
381 applied for both analytical approaches.

382 **Adjustment for informative censoring at treatment discontinuation in the PP analysis:** In the
383 per-protocol analysis described above, patients will be censored when they initiate another treatment.
384 Implicit in the per-protocol analysis is an assumption that censoring is independent of the studied
385 outcome, so that this differential treatment selection should not introduce bias.

386 In this analysis, we will adjust for potential selection bias via informative censoring, by reweighting
387 patient observations using the inverse of the probability of being censored at the initiation of another
388 treatment conditional on the same confounders selected at baseline (i.e., outcome risk factors
389 potentially associated with treatment initiation) but updating their values during follow-up. (Hernan et
390 al., 2000; Robins et al., 2000)

391

392 Analyses will be done using SAS Enterprise Guide 7.1 software.

393

394 **4.7.5. Sample size**

395 The sample size will be driven by the availability of individuals with exposures and outcomes within
396 each database and no *a priori* sample size requirement will be stipulated.

397

398 **4.8. Quality control**

399 The study will be conducted according to the ENCePP code of conduct (European Medicines Agency
400 2018).

401 Standard operating procedures or internal process guidance will be adhered to for the conduct of the
402 study. These procedures include rules for secure and confidential data storage, quality-control
403 procedures for all aspects of the study from protocol development to the reporting of the results.

404 All documents will undergo at least one round a review by an experienced reviewer, while the results
405 from the statistical analysis will be either reviewed or checked via double coding.

406 The quality control of the data is the responsibility of the data holder.

407 **4.9. Limitations of the research methods**

408 Exposure misclassification may exist since neither OTC drug use nor medication use during
409 hospitalisation are captured in the included databases. This is a particular issue because of the availability
410 of OTC PPIs has increased over time (Johnson et al., 2017) and, probably their OTC use. Additionally,
411 information on the actual duration of treatment corresponding to each prescription is not available and
412 is difficult to estimate since patients may be prescribed large packs and instructed to use the drug as
413 needed, with possible discontinuation/restart and dose-variation over time. Moreover, whether patients
414 collected their prescriptions or consumed the prescribed medication is unknown. Due to this uncertainty
415 and considering information from individual case reports about the latency of effect, we chose to follow
416 patients for a maximum of one year and attribute the entire follow-up to the index treatment unless
417 another treatment was initiated. It should be noted that, in the analysis comparing with non-initiators,
418 we restricted the study population to patients with chronic indications, for which treatment is likely
419 chronic.

420 To our knowledge, the accuracy of diagnostic coding for sexual dysfunction has not been assessed in the
421 primary care databases available. However, the nature of the diagnosis means that its recording in
422 primary care records could be reasonably accurate, particularly for sexual dysfunction in male individuals.
423 Nonetheless, this assumption should be treated cautiously. In the UK, the patent for Viagra expired in
424 June 2013, which followed a drop by 93% in the price of generic preparations of sildenafil compared to
425 the price of branded Viagra (Connelly, 2017). Besides, Sildenafil has been available OTC without
426 prescription from UK pharmacies since 2017 and, therefore, patients have no longer needed to see their
427 doctor to get a diagnosis ever since. (MHRA, 2017) These events led to marked changes in diagnosis
428 coding practices of erectile dysfunction during 2013-2014 and marked decrease of coding for impotence
429 by GPs since 2017 which are reflected in the distribution of outcome events over calendar time. In
430 IQVIA™ DA Germany the reporting of male sexual dysfunction appears stable after 2005. To account for
431 uncertainties around potential misclassification due to changes in diagnostic criteria or coding practices
432 over time, calendar period will be adjusted for in the analysis.

433 It also needs to be considered that patient's medical history, as captured by GP practices included in
434 the study, may be incomplete, particularly in the IQVIA DA Germany database. In Germany, there is
435 no mandatory GP system and patients have free doctor choice. A specialist can be consulted without
436 referral from the GP. As a result, data are collected from visits to various medical practices which are
437 not linked by a unique patient identifier. Therefore, the entire medical history of patients might be
438 fragmented and for that reason there is a risk of exposure, outcome and covariates misclassification.
439 However, this misclassification will affect both target and comparator groups.

440 Although confounding by indication represents a common source of bias, it is not likely that the main
441 indications for PPIs (i.e., gastroesophageal reflux disease, esophagitis, and treatment for or prophylaxis
442 against gastric or duodenal ulcer disease) are strongly associated with SD.

443 Ideally, the active comparator should be known to have no effect on the event of interest. Impotence is
444 currently listed as a rare side effect in the UK product information for lansoprazole (EMC, 2023, 2024b),
445 and for H2RAs. (EMC, 2024a, 2024c) Therefore, we will use multiple comparators, including non-
446 initiators, which is meant to capture (if possible) a “background risk” among patients with the indication
447 but not under treatment. Even though we will impose the presence of at least one chronic indication for
448 PPIs/H2RAs to both initiators and non-initiators, it is possible that non-initiators differ from initiators in
449 the distribution of unmeasured outcome risk factors, which would leave residual unadjusted confounding.
450 In addition, non-initiators might include patients misclassified as untreated but who were users of OTC
451 drugs. However, we assume that OTC use is episodic, i.e., occurring occasionally at irregular intervals
452 and therefore, individuals might be less exposed to long-term treatments.

453 Finally, although more than 50 potential confounders will be adjusted for, we cannot rule out the
454 possibility of residual confounding as not all relevant potential confounders are captured in the selected
455 databases (e.g., other comorbid conditions or severity of comorbidities) and there might be
456 misclassification of measured covariates due to incomplete capture of some co-morbidities or co-
457 medication in GP data.

458

459 **5. Protection of human subjects**

460 Patient confidentiality will be protected according to the EU General Data Protection Regulation (GDPR)
461 on the protection of individuals.

462 In accordance with database rules on the management of low cell counts, cells with low numbers (<6
463 in the IMRD database) will be removed prior to publication of the final study report. Additional cells
464 may be redacted (events/patients typically being rounded up to the nearest 10) if needed in order to
465 ensure that the aforementioned low cell counts cannot be re-identified. This may include both
466 events/patients and follow-up times.

467

468 **6. Management and reporting of adverse events/adverse** 469 **reactions**

